11.2. Formulae for Estimated Glomerular Filtration Rate Calculation

Estimated glomerular filtration rate (eGFR; in mL/min/1.73m²) will be calculated from serum creatinine (SCr) based on the Modification of Diet in Renal Disease formula for patients ≥18 years of age and the Schwartz Bedside Formula for patients <18 years of age.

Modification of Diet in Renal Disease Formula [10]

- Conventional units
 - $eGFR \text{ (mL/min/1.73m}^2\text{)} = 175 \times (\text{SCr [mg/dL]})^{-1.154} \times (\text{age})^{-0.203} \times (0.742, \text{ if female), or } \times (1.212, \text{ if African American})$
- SI units
 - $eGFR \text{ (mL/min/1.73m}^2\text{)} = 175 \times (\text{SCr } [\mu\text{mol/L}]/88.4)^{-1.154} \times (\text{age})^{-0.203} \times (0.742, \text{ if female), or } \times (1.212, \text{ if African American})$

Schwartz Bedside Formula [11]

- Conventional units
 - $eGFR \text{ (mL/min/1.73 m}^2\text{)} = (0.413 \times \text{height [cm]})/\text{Scr (mg/dL)}$
- SI units
 - $eGFR \text{ (mL/min/1.73 m}^2\text{)} = (36.2 \times \text{height [cm]})/\text{Scr } (\mu\text{mol/L)}$

11.3. Blood Volume Limits in Pediatric Patients (Part B)

The maximum blood volume, which will be collected from pediatric patients in Part B over the course of the study, will be based on age and weight and will not exceed those specified in [Table 13](#), which was adapted from the Human Subject Protection Program Guidance Document.

Table 13: Maximum Allowable Total Blood Collection Volumes Chart (Part B)

Body Weight (kg)	Body Weight (lbs)	Total blood volume (mL)	Maximum allowable volume in a 24 hour period		Total volume collected in a 30-day period	
			2.5% of total blood volume (mL)	3% of total blood volume (mL)	5% of total blood volume (mL)	10% of total blood volume (mL)
1	2.2	100	2.5	3	5	10
2	4.4	200	5	6	10	20
3	6.6	240	6	7.2	12	24
4	8.8	320	8	9.6	16	32
5	11	400	10	12	20	40
6	13.2	480	12	14.4	24	48
7	15.4	560	14	16.8	28	56
8	17.6	640	16	19.2	32	64
9	19.8	720	18	21.6	36	72
10	22	800	20	24	40	80
11-15	24-33	880-1200	22-30	26.4-36	44-60	88-120
16-20	35-44	1280-1600	32-40	38.4-48	64-80	128-160
21-25	46-55	1680-2000	42-50	50.4-60	64-100	168-200
26-30	57-66	2080-2400	52-60	62.4-72	104-120	208-240
31-35	68-77	2480-2800	62-70	74.4-84	124-140	248-280
36-40	79-88	2880-3200	72-80	86.4-96	144-160	288-320
41-45	90-99	3280-3600	82-90	98.4-108	164-180	328-3600
46-50	101-110	3680-4000	92-100	110.4-120	184-200	368-400
51-55	112-121	4080-4400	102-110	122.4-132	204-220	408-440
56-60	123-132	4480-4800	112-120	134.4-144	224-240	448-480
61-65	134-143	4880-5200	122-130	146.4-156	244-260	488-520
66-70	145-154	5280-5600	132-140	158.4-168	264-280	528-560
71-75	156-165	5680-6000	142-150	170.4-180	284-300	568-600
76-80	167-176	6080-6400	152-160	182.4-192	304-360	608-640
81-85	178-187	6480-6800	162-170	194.4-204	324-340	648-680
86-90	189-198	6880-7200	172-180	206.4-216	344-360	688-720
91-95	200-209	7280-7600	182-190	218.4-228	364-380	728-760
96-100	211-220	7680-8000	192-200	230.4-240	384-400	768-800

Adapted from <http://www.feinsteininstitute.org/wp-content/uploads/2013/03/Recruitment-Methods-for-Clinical-Research-Studies.pdf>. [12]

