7.5.6.4. Maximum Blood Volume

The maximum blood volume for subjects in Part A will not exceed 500 mL over the course of the study.

In Part B, the maximum blood volume, which will be collected from pediatric patients over the course of the study, will be based on age and weight and will not exceed those specified in [Table 13](#) from the Feinstein Institute for Medical Research Human Subject Protection Program Guidance Document (Section 11.3 in the Appendix).[12] The maximum blood volume for adult and pediatric patients initially randomized to ALN-GO1 is not expected to exceed 400 mL over the course of the study. The maximum blood volume for adult and pediatric patients initially randomized to placebo is not expected to exceed 450 mL over the course of the study. The blood volume limits for patients in Part B are based on those for 6 year old girls in the 5th percentile for weight, the smallest patients who may be enrolled in the study.

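### Three 30-day limits in the pediatric blood-volume table (Protocol Table 13) do not equal their stated percentage of the blood volume in the same row

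*Protocol*

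**What the plan says.** Section 11.3 makes Table 13 the ceiling for pediatric collection in Part B: the volume "will be based on age and weight and will not exceed those specified in" that table. Section 7.5.6.4 repeats the commitment. Table 9 (area E) also rules out exceeding the maximum volume, although it points to age and weight guidelines and to Section 7 rather than to Table 13 by name. Footnote v of Table 2, footnote r of Table 3 and footnote v of Table 4 use the Table 13 limits to decide when certain exploratory blood samples become optional for a child.

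Table 13 gives weight in kg and lb, total blood volume, two 24-hour limits (2.5% and 3% of blood volume) and two 30-day limits (5% and 10%). The rows at issue, in that column order, are:

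- "21-25 46-55 1680-2000 42-50 50.4-60 64-100 168-200"
- "41-45 90-99 3280-3600 82-90 98.4-108 164-180 328-3600"
- "76-80 167-176 6080-6400 152-160 182.4-192 304-360 608-640"

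The next heavier band after the last of these, which is correct, reads "81-85 178-187 6480-6800 162-170 194.4-204 324-340 648-680".

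Section 7.5.6.4 adds context. The Part B limits "are based on those for 6 year old girls in the 5th percentile for weight". Expected collection for patients first randomized to ALN-GO1 "is not expected to exceed 400 mL over the course of the study"; for those first randomized to placebo it "is not expected to exceed 450 mL over the course of the study".

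**The concern.** Each limit should be the column percentage multiplied by the blood volume in the same row, and no limit should fall as weight rises. Three 30-day entries break both rules.

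The table is an operating threshold. Sites must look up a child's row to know whether the cap has been reached and whether an exploratory sample may be skipped. A cell that is too high weakens a child-protection limit. A cell that is too low could make a sample optional without cause. The stake is the correctness of that lookup; no safety, PK or PD analysis depends on these numbers.

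**Working it through.** **Inputs.** All come from Table 13: total blood volume in each row, the four column percentages and the printed limits. There are 10 single-weight rows (1 to 10 kg) and 18 range rows (11-15 to 96-100 kg). The number of printed limits is 10 × 4 + 18 × 4 × 2 = 184.

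**Formula.** Limit = column percentage × total blood volume, applied at each printed end of each row.

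**Reproducing the table.** 181 of the 184 values match exactly, including those with a decimal, so rounding does not explain the rest. The three that fail are:

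| Row end | Column | Blood volume (mL) | Recomputed (mL) | Printed (mL) | Printed as % of blood volume | Error |
|---|---|---|---|---|---|---|
| 21 kg | 5%, 30 days | 1680 | 0.05 × 1680 = 84 | 64 | 64/1680 = 3.8% | 20 mL too strict |
| 45 kg | 10%, 30 days | 3600 | 0.10 × 3600 = 360 | 3600 | 3600/3600 = 100% | ten times too high |
| 80 kg | 5%, 30 days | 6400 | 0.05 × 6400 = 320 | 360 | 360/6400 = 5.6% | 40 mL too loose |

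The other end of each of these ranges is right: 0.05 × 2000 = 100, 0.10 × 3280 = 328 and 0.05 × 6080 = 304.

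**Is the blood-volume column the source?** No. It equals 80 mL/kg at every row end from 3 kg up, including the affected rows: 1680/21 = 2000/25 = 3280/41 = 3600/45 = 6080/76 = 6400/80 = 80. (The 1 and 2 kg rows use 100 mL/kg, which does not matter here.) The remaining limits in the three rows, including all their 24-hour limits, agree with the printed blood volumes.

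**A check that does not use the column percentages.** Reading each of the four limit columns in order of rising weight, a limit falls in only three places, all caused by these cells:

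- 5% column, 20 to 21 kg: 80 falls to 64 mL.
- 10% column, 45 to 46 kg: 3600 falls to 368 mL.
- 5% column, 80 to 81 kg: 360 falls to 324 mL. The 360 mL printed for 80 kg exceeds the whole 324-340 mL range of the 81-85 kg band.

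**Could the cells bind?** The protocol gives no per-visit blood volumes, so this cannot be settled. For the two loose cells, the whole-study expectation gives a sense of scale. Reaching the corrected 320 mL within 30 days would take 320/450 = 71% to 320/400 = 80% of the expected total; reaching 360 mL would take 360/450 = 80% to 360/400 = 90%.

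**The case against.** The arithmetic is not in dispute. The case against the point rests on four arguments.

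1. **It may be a reading error.** Two of the mismatches are single-digit substitutions (8 and 6, 2 and 6) and the third is one extra zero. Text taken from a PDF can contain such slips, and the documents alone cannot distinguish them from a sponsor typo. This stands as a caution and is why the first step is to look at the original page. Against it, the other 181 values came through exactly.

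2. **The source chart is not available.** Table 13 is adapted from an outside document, so the slips may have been inherited. That affects who made the error. It does not affect whether the table contradicts its own column definitions, and the sponsor has adopted the table as its limit.

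3. **The three cells cannot all be operative together.** The table gives two 30-day limits and the protocol does not say which governs. Under the 5% column the 3600 mL entry is inert; under the 10% column the 64 and 360 mL entries are. This is correct and reduces the count of operative errors to two or one. It does not reduce it to zero under either reading.

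4. **The loose cells are very unlikely to bind.** Collection was planned around the smallest eligible children, the 24-hour limits are correct, and the expected total is 400 to 450 mL spread over a schedule running to at least Day 141. A site would also recognise 3600 mL as impossible. All of this stands. The entry with the most plausible practical effect is 64 mL, since a young child may well weigh about 21 kg (an assumption, as the protocol gives no weight distribution), and that entry errs on the safe side.

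**Conclusion.** The concern holds. On the text as supplied, three of 184 limits in Table 13 contradict the percentage that defines their column: one is 20 mL too strict (21 kg), one is ten times too high (45 kg) and one is 40 mL too loose (80 kg). Two independent checks, the column percentages and the ordering by weight, pick out the same three cells.

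The conclusion assumes that the extracted digits match the printed page and that the column headings mean what they say. The importance is minor. No unsafe draw and no effect on a safety, PK or PD endpoint is shown. It is worth correcting because the protocol treats the table as a cap and uses it to decide which samples may be omitted.

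**What to change.** Compare the three cells with the original page. If they are printed as shown, correct them as follows and reissue the table to sites:

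- 21-25 kg, 5% column: 84-100 mL.
- 41-45 kg, 10% column: 328-360 mL.
- 76-80 kg, 5% column: 304-320 mL.

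It would help to state at the same time which of the two 30-day columns is the operative cap, because the protocol does not say. The cost of correcting the cells is an administrative change letter or a line in the next amendment. No procedure, visit or analysis changes.

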11.4. Normative Pediatric Blood Pressure Tables

For pediatric patients <18 years old, study entry criteria for blood pressure will be determined according to normative blood pressure tables based on normal-weight children included in published guidelines issued by the American Academy of Pediatrics [13] (see [Table 14](#) and [Table 15](#)). Patients will be excluded if diastolic and/or systolic blood pressure is equal to or greater than the 95th percentile for sex, age, and height (mean of screening height measurements).

Table 14: Blood Pressure Levels for Girls by Age and Height Percentile

Age (y)	BP Percentile	SBP (mm Hg)							DBP (mm Hg)						
		Height Percentile or Measured Height							Height Percentile or Measured Height						
		5%	10%	25%	50%	75%	90%	95%	5%	10%	25%	50%	75%	90%	95%
1	Height (in)	29.7	30.2	30.9	31.8	32.7	33.4	33.9	29.7	30.2	30.9	31.8	32.7	33.4	33.9
	Height (cm)	75.4	76.6	78.6	80.8	83	84.9	86.1	75.4	76.6	78.6	80.8	83	84.9	86.1
	50th	84	85	86	86	87	88	88	41	42	42	43	44	45	46
	90th	98	99	99	100	101	102	102	54	55	56	56	57	58	58
	95th	101	102	102	103	104	105	105	59	59	60	60	61	62	62
2	95th + 12 mm Hg	113	114	114	115	116	117	117	71	71	72	72	73	74	74
	Height (in)	33.4	34	34.9	35.9	36.9	37.8	38.4	33.4	34	34.9	35.9	36.9	37.8	38.4
	Height (cm)	84.9	86.3	88.6	91.1	93.7	96	97.4	84.9	86.3	88.6	91.1	93.7	96	97.4
	50th	87	87	88	89	90	91	91	45	46	47	48	49	50	51
	90th	101	101	102	103	104	105	106	58	58	59	60	61	62	62
3	95th	104	105	106	106	107	108	109	62	63	63	64	65	66	66
	95th + 12 mm Hg	116	117	118	118	119	120	121	74	75	75	76	77	78	78
	Height (in)	35.8	36.4	37.3	38.4	39.6	40.6	41.2	35.8	36.4	37.3	38.4	39.6	40.6	41.2
	Height (cm)	91	92.4	94.9	97.6	100.5	103.1	104.6	91	92.4	94.9	97.6	100.5	103.1	104.6
	50th	88	89	89	90	91	92	93	48	48	49	50	51	53	53
4	90th	102	103	104	104	105	106	107	60	61	61	62	63	64	65
	95th	106	106	107	108	109	110	110	64	65	65	66	67	68	69
	95th + 12 mm Hg	118	118	119	120	121	122	122	76	77	77	78	79	80	81
	Height (in)	38.3	38.9	39.9	41.1	42.4	43.5	44.2	38.3	38.9	39.9	41.1	42.4	43.5	44.2
	Height (cm)	97.2	98.8	101.4	104.5	107.6	110.5	112.2	97.2	98.8	101.4	104.5	107.6	110.5	112.2
5	50th	89	90	91	92	93	94	94	50	51	51	53	54	55	55
	90th	103	104	105	106	107	108	108	62	63	64	65	66	67	67
	95th	107	108	109	109	110	111	112	66	67	68	69	70	70	71
	95th + 12 mm Hg	119	120	121	121	122	123	124	78	79	80	81	82	82	83
	Height (in)	40.8	41.5	42.6	43.9	45.2	46.5	47.3	40.8	41.5	42.6	43.9	45.2	46.5	47.3
6	Height (cm)	103.6	105.3	108.2	111.5	114.9	118.1	120	103.6	105.3	108.2	111.5	114.9	118.1	120
	50th	90	91	92	93	94	95	96	52	52	53	55	56	57	57
	90th	104	105	106	107	108	109	110	64	65	66	67	68	69	70
	95th	108	109	109	110	111	112	113	68	69	70	71	72	73	73
	95th + 12 mm Hg	120	121	121	122	123	124	125	80	81	82	83	84	85	85
7	Height (in)	43.3	44	45.2	46.6	48.1	49.4	50.3	43.3	44	45.2	46.6	48.1	49.4	50.3
	Height (cm)	110	111.8	114.9	118.4	122.1	125.6	127.7	110	111.8	114.9	118.4	122.1	125.6	127.7
	50th	92	92	93	94	96	97	97	54	54	55	56	57	58	59
	90th	105	106	107	108	109	110	111	67	67	68	69	70	71	71
	95th	109	109	110	111	112	113	114	70	71	72	72	73	74	74
8	95th + 12 mm Hg	121	121	122	123	124	125	126	82	83	84	84	85	86	86
	Height (in)	45.6	46.4	47.7	49.2	50.7	52.1	53	45.6	46.4	47.7	49.2	50.7	52.1	53
	Height (cm)	115.9	117.8	121.1	124.9	128.8	132.5	134.7	115.9	117.8	121.1	124.9	128.8	132.5	134.7
	50th	92	93	94	95	97	98	99	55	55	56	57	58	59	60
	90th	106	106	107	109	110	111	112	68	68	69	70	71	72	72
9	95th	109	110	111	112	113	114	115	72	72	73	73	74	74	75
	95th + 12 mm Hg	121	122	123	124	125	126	127	84	84	85	85	86	86	87

Age (y)	BP Percentile	SBP (mm Hg)								DBP (mm Hg)					
		Height Percentile or Measured Height								Height Percentile or Measured Height					
		5%	10%	25%	50%	75%	90%	95%	5%	10%	25%	50%	75%	90%	95%
8	Height (in)	47.6	48.4	49.8	51.4	53	54.5	55.5	47.6	48.4	49.8	51.4	53	54.5	55.5
	Height (cm)	121	123	126.5	130.6	134.7	138.5	140.9	121	123	126.5	130.6	134.7	138.5	140.9
	50th	93	94	95	97	98	99	100	56	56	57	59	60	61	61
	90th	107	107	108	110	111	112	113	69	70	71	72	72	73	73
	95th	110	111	112	113	115	116	117	72	73	74	74	75	75	75
	95th + 12 mm Hg	122	123	124	125	127	128	129	84	85	86	86	87	87	87
9	Height (in)	49.3	50.2	51.7	53.4	55.1	56.7	57.7	49.3	50.2	51.7	53.4	55.1	56.7	57.7
	Height (cm)	125.3	127.6	131.3	135.6	140.1	144.1	146.6	125.3	127.6	131.3	135.6	140.1	144.1	146.6
	50th	95	95	97	98	99	100	101	57	58	59	60	60	61	61
	90th	108	108	109	111	112	113	114	71	71	72	73	73	73	73
	95th	112	112	113	114	116	117	118	74	74	75	75	75	75	75
	95th + 12 mm Hg	124	124	125	126	128	129	130	86	86	87	87	87	87	87
10	Height (in)	51.1	52	53.7	55.5	57.4	59.1	60.2	51.1	52	53.7	55.5	57.4	59.1	60.2
	Height (cm)	129.7	132.2	136.3	141	145.8	150.2	152.8	129.7	132.2	136.3	141	145.8	150.2	152.8
	50th	96	97	98	99	101	102	103	58	59	59	60	61	61	62
	90th	109	110	111	112	113	115	116	72	73	73	73	73	73	73
	95th	113	114	114	116	117	119	120	75	75	76	76	76	76	76
	95th + 12 mm Hg	125	126	126	128	129	131	132	87	87	88	88	88	88	88
11	Height (in)	53.4	54.5	56.2	58.2	60.2	61.9	63	53.4	54.5	56.2	58.2	60.2	61.9	63
	Height (cm)	135.6	138.3	142.8	147.8	152.8	157.3	160	135.6	138.3	142.8	147.8	152.8	157.3	160
	50th	98	99	101	102	104	105	106	60	60	60	61	62	63	64
	90th	111	112	113	114	116	118	120	74	74	74	74	74	75	75
	95th	115	116	117	118	120	123	124	76	77	77	77	77	77	77
	95th + 12 mm Hg	127	128	129	130	132	135	136	88	89	89	89	89	89	89
12	Height (in)	56.2	57.3	59	60.9	62.8	64.5	65.5	56.2	57.3	59	60.9	62.8	64.5	65.5
	Height (cm)	142.8	145.5	149.9	154.8	159.6	163.8	166.4	142.8	145.5	149.9	154.8	159.6	163.8	166.4
	50th	102	102	104	105	107	108	108	61	61	61	62	64	65	65
	90th	114	115	116	118	120	122	122	75	75	75	75	76	76	76
	95th	118	119	120	122	124	125	126	78	78	78	78	79	79	79
	95th + 12 mm Hg	130	131	132	134	136	137	138	90	90	90	90	91	91	91
13	Height (in)	58.3	59.3	60.9	62.7	64.5	66.1	67	58.3	59.3	60.9	62.7	64.5	66.1	67
	Height (cm)	148.1	150.6	154.7	159.2	163.7	167.8	170.2	148.1	150.6	154.7	159.2	163.7	167.8	170.2
	50th	104	105	106	107	108	108	109	62	62	63	64	65	65	66
	90th	116	117	119	121	122	123	123	75	75	75	76	76	76	76
	95th	121	122	123	124	126	126	127	79	79	79	79	80	80	81
	95th + 12 mm Hg	133	134	135	136	138	138	139	91	91	91	91	92	92	93
14	Height (in)	59.3	60.2	61.8	63.5	65.2	66.8	67.7	59.3	60.2	61.8	63.5	65.2	66.8	67.7
	Height (cm)	150.6	153	156.9	161.3	165.7	169.7	172.1	150.6	153	156.9	161.3	165.7	169.7	172.1
	50th	105	106	107	108	109	109	109	63	63	64	65	66	66	66
	90th	118	118	120	122	123	123	123	76	76	76	76	77	77	77
	95th	123	123	124	125	126	127	127	80	80	80	80	81	81	82
	95th + 12 mm Hg	135	135	136	137	138	139	139	92	92	92	92	93	93	94

Age (y)	BP Percentile	SBP (mm Hg)								DBP (mm Hg)					
		Height Percentile or Measured Height								Height Percentile or Measured Height					
		5%	10%	25%	50%	75%	90%	95%	5%	10%	25%	50%	75%	90%	95%
15	Height (in)	59.7	60.6	62.2	63.9	65.6	67.2	68.1	59.7	60.6	62.2	63.9	65.6	67.2	68.1
	Height (cm)	151.7	154	157.9	162.3	166.7	170.6	173	151.7	154	157.9	162.3	166.7	170.6	173
	50th	105	106	107	108	109	109	109	64	64	64	65	66	67	67
	90th	118	119	121	122	123	123	124	76	76	76	77	77	78	78
	95th	124	124	125	126	127	127	128	80	80	80	81	82	82	82
	95th + 12 mm Hg	136	136	137	138	139	139	140	92	92	92	93	94	94	94
16	Height (in)	59.9	60.8	62.4	64.1	65.8	67.3	68.3	59.9	60.8	62.4	64.1	65.8	67.3	68.3
	Height (cm)	152.1	154.5	158.4	162.8	167.1	171.1	173.4	152.1	154.5	158.4	162.8	167.1	171.1	173.4
	50th	106	107	108	109	109	110	110	64	64	65	66	66	67	67
	90th	119	120	122	123	124	124	124	76	76	76	77	78	78	78
	95th	124	125	125	127	127	128	128	80	80	80	81	82	82	82
	95th + 12 mm Hg	136	137	137	139	139	140	140	92	92	92	93	94	94	94
17	Height (in)	60.0	60.9	62.5	64.2	65.9	67.4	68.4	60.0	60.9	62.5	64.2	65.9	67.4	68.4
	Height (cm)	152.4	154.7	158.7	163.0	167.4	171.3	173.7	152.4	154.7	158.7	163.0	167.4	171.3	173.7
	50th	107	108	109	110	110	110	111	64	64	65	66	66	66	67
	90th	120	121	123	124	124	125	125	76	76	77	77	78	78	78
	95th	125	125	126	127	128	128	128	80	80	80	81	82	82	82
	95th + 12 mm Hg	137	137	138	139	140	140	140	92	92	92	93	94	94	94

Adapted from Flynn et al. 2017 [13]

Table 15: Blood Pressure Levels for Boys by Age and Height Percentile

Age (y)	BP Percentile	SBP (mm Hg)							DBP (mm Hg)						
		Height Percentile or Measured Height													
		5%	10%	25%	50%	75%	90%	95%	5%	10%	25%	50%	75%	90%	95%
1	Height (in)	30.4	30.8	31.6	32.4	33.3	34.1	34.6	30.4	30.8	31.6	32.4	33.3	34.1	34.6
	Height (cm)	77.2	78.3	80.2	82.4	84.6	86.7	87.9	77.2	78.3	80.2	82.4	84.6	86.7	87.9
	50th	85	85	86	86	87	88	88	40	40	40	41	41	42	42
	90th	98	99	99	100	100	101	101	52	52	53	53	54	54	54
	95th	102	102	103	103	104	105	105	54	54	55	55	56	57	57
	95th + 12 mm Hg	114	114	115	115	116	117	117	66	66	67	67	68	69	69
2	Height (in)	33.9	34.4	35.3	36.3	37.3	38.2	38.8	33.9	34.4	35.3	36.3	37.3	38.2	38.8
	Height (cm)	86.1	87.4	89.6	92.1	94.7	97.1	98.5	86.1	87.4	89.6	92.1	94.7	97.1	98.5
	50th	87	87	88	89	89	90	91	43	43	44	44	45	46	46
	90th	100	100	101	102	103	103	104	55	55	56	56	57	58	58
	95th	104	105	105	106	107	107	108	57	58	58	59	60	61	61
	95th + 12 mm Hg	116	117	117	118	119	119	120	69	70	70	71	72	73	73
3	Height (in)	36.4	37	37.9	39	40.1	41.1	41.7	36.4	37	37.9	39	40.1	41.1	41.7
	Height (cm)	92.5	93.9	96.3	99	101.8	104.3	105.8	92.5	93.9	96.3	99	101.8	104.3	105.8
	50th	88	89	89	90	91	92	92	45	46	46	47	48	49	49
	90th	101	102	102	103	104	105	105	58	58	59	59	60	61	61
	95th	106	106	107	107	108	109	109	60	61	61	62	63	64	64
	95th + 12 mm Hg	118	118	119	119	120	121	121	72	73	73	74	75	76	76
4	Height (in)	38.8	39.4	40.5	41.7	42.9	43.9	44.5	38.8	39.4	40.5	41.7	42.9	43.9	44.5
	Height (cm)	98.5	100.2	102.9	105.9	108.9	111.5	113.2	98.5	100.2	102.9	105.9	108.9	111.5	113.2
	50th	90	90	91	92	93	94	94	48	49	49	50	51	52	52
	90th	102	103	104	105	105	106	107	60	61	62	62	63	64	64
	95th	107	107	108	108	109	110	110	63	64	65	66	67	67	68
	95th + 12 mm Hg	119	119	120	120	121	122	122	75	76	77	78	79	79	80
5	Height (in)	41.1	41.8	43.0	44.3	45.5	46.7	47.4	41.1	41.8	43.0	44.3	45.5	46.7	47.4
	Height (cm)	104.4	106.2	109.1	112.4	115.7	118.6	120.3	104.4	106.2	109.1	112.4	115.7	118.6	120.3
	50th	91	92	93	94	95	96	96	51	51	52	53	54	55	55
	90th	103	104	105	106	107	108	108	63	64	65	65	66	67	67
	95th	107	108	109	109	110	111	112	66	67	68	69	70	70	71
	95th + 12 mm Hg	119	120	121	121	122	123	124	78	79	80	81	82	82	83
6	Height (in)	43.4	44.2	45.4	46.8	48.2	49.4	50.2	43.4	44.2	45.4	46.8	48.2	49.4	50.2
	Height (cm)	110.3	112.2	115.3	118.9	122.4	125.6	127.5	110.3	112.2	115.3	118.9	122.4	125.6	127.5
	50th	93	93	94	95	96	97	98	54	54	55	56	57	57	58
	90th	105	105	106	107	109	110	110	66	66	67	68	68	69	69
	95th	108	109	110	111	112	113	114	69	70	70	71	72	72	73
	95th + 12 mm Hg	120	121	122	123	124	125	126	81	82	82	83	84	84	85
7	Height (in)	45.7	46.5	47.8	49.3	50.8	52.1	52.9	45.7	46.5	47.8	49.3	50.8	52.1	52.9
	Height (cm)	116.1	118	121.4	125.1	128.9	132.4	134.5	116.1	118	121.4	125.1	128.9	132.4	134.5
	50th	94	94	95	97	98	98	99	56	56	57	58	58	59	59
	90th	106	107	108	109	110	111	111	68	68	69	70	70	71	71
	95th	110	110	111	112	114	115	116	71	71	72	73	73	74	74
	95th + 12 mm Hg	122	122	123	124	126	127	128	83	83	84	85	85	86	86

Age (y)	BP Percentile	SBP (mm Hg)							DBP (mm Hg)						
		Height Percentile or Measured Height							Height Percentile or Measured Height						
		5%	10%	25%	50%	75%	90%	95%	5%	10%	25%	50%	75%	90%	95%
8	Height (in)	47.8	48.6	50	51.6	53.2	54.6	55.5	47.8	48.6	50	51.6	53.2	54.6	55.5
	Height (cm)	121.4	123.5	127	131	135.1	138.8	141	121.4	123.5	127	131	135.1	138.8	141
	50th	95	96	97	98	99	99	100	57	57	58	59	59	60	60
	90th	107	108	109	110	111	112	112	69	70	70	71	72	72	73
	95th	111	112	112	114	115	116	117	72	73	73	74	75	75	75
	95th + 12 mm Hg	123	124	124	126	127	128	129	84	85	85	86	87	87	87
9	Height (in)	49.6	50.5	52	53.7	55.4	56.9	57.9	49.6	50.5	52	53.7	55.4	56.9	57.9
	Height (cm)	126	128.3	132.1	136.3	140.7	144.7	147.1	126	128.3	132.1	136.3	140.7	144.7	147.1
	50th	96	97	98	99	100	101	101	57	58	59	60	61	62	62
	90th	107	108	109	110	112	113	114	70	71	72	73	74	74	74
	95th	112	112	113	115	116	118	119	74	74	75	76	76	77	77
	95th + 12 mm Hg	124	124	125	127	128	130	131	86	86	87	88	88	89	89
10	Height (in)	51.3	52.2	53.8	55.6	57.4	59.1	60.1	51.3	52.2	53.8	55.6	57.4	59.1	60.1
	Height (cm)	130.2	132.7	136.7	141.3	145.9	150.1	152.7	130.2	132.7	136.7	141.3	145.9	150.1	152.7
	50th	97	98	99	100	101	102	103	59	60	61	62	63	63	64
	90th	108	109	111	112	113	115	116	72	73	74	74	75	75	76
	95th	112	113	114	116	118	120	121	76	76	77	77	78	78	78
	95th + 12 mm Hg	124	125	126	128	130	132	133	88	88	89	89	90	90	90
11	Height (in)	53	54	55.7	57.6	59.6	61.3	62.4	53	54	55.7	57.6	59.6	61.3	62.4
	Height (cm)	134.7	137.3	141.5	146.4	151.3	155.8	158.6	134.7	137.3	141.5	146.4	151.3	155.8	158.6
	50th	99	99	101	102	103	104	106	61	61	62	63	63	63	63
	90th	110	111	112	114	116	117	118	74	74	75	75	75	76	76
	95th	114	114	116	118	120	123	124	77	78	78	78	78	78	78
	95th + 12 mm Hg	126	126	128	130	132	135	136	89	90	90	90	90	90	90
12	Height (in)	55.2	56.3	58.1	60.1	62.2	64	65.2	55.2	56.3	58.1	60.1	62.2	64	65.2
	Height (cm)	140.3	143	147.5	152.7	157.9	162.6	165.5	140.3	143	147.5	152.7	157.9	162.6	165.5
	50th	101	101	102	104	106	108	109	61	62	62	62	62	63	63
	90th	113	114	115	117	119	121	122	75	75	75	75	75	76	76
	95th	116	117	118	121	124	126	128	78	78	78	78	78	79	79
	95th + 12 mm Hg	128	129	130	133	136	138	140	90	90	90	90	90	91	91
13	Height (in)	57.9	59.1	61	63.1	65.2	67.1	68.3	57.9	59.1	61	63.1	65.2	67.1	68.3
	Height (cm)	147	150	154.9	160.3	165.7	170.5	173.4	147	150	154.9	160.3	165.7	170.5	173.4
	50th	103	104	105	108	110	111	112	61	60	61	62	63	64	65
	90th	115	116	118	121	124	126	126	74	74	74	75	76	77	77
	95th	119	120	122	125	128	130	131	78	78	78	78	80	81	81
	95th + 12 mm Hg	131	132	134	137	140	142	143	90	90	90	90	92	93	93
14	Height (in)	60.6	61.8	63.8	65.9	68.0	69.8	70.9	60.6	61.8	63.8	65.9	68.0	69.8	70.9
	Height (cm)	153.8	156.9	162	167.5	172.7	177.4	180.1	153.8	156.9	162	167.5	172.7	177.4	180.1
	50th	105	106	109	111	112	113	113	60	60	62	64	65	66	67
	90th	119	120	123	126	127	128	129	74	74	75	77	78	79	80
	95th	123	125	127	130	132	133	134	77	78	79	81	82	83	84
	95th + 12 mm Hg	135	137	139	142	144	145	146	89	90	91	93	94	95	96

Age (y)	BP Percentile	SBP (mmHg)								DBP (mmHg)					
		Height Percentile or Measured Height								Height Percentile or Measured Height					
		5%	10%	25%	50%	75%	90%	95%	5%	10%	25%	50%	75%	90%	95%
15	Height (in)	62.6	63.8	65.7	67.8	69.8	71.5	72.5	62.6	63.8	65.7	67.8	69.8	71.5	72.5
	Height (cm)	159	162	166.9	172.2	177.2	181.6	184.2	159	162	166.9	172.2	177.2	181.6	184.2
	50th	108	110	112	113	114	114	114	61	62	64	65	66	67	68
	90th	123	124	126	128	129	130	130	75	76	78	79	80	81	81
	95th	127	129	131	132	134	135	135	78	79	81	83	84	85	85
	95th + 12 mmHg	139	141	143	144	146	147	147	90	91	93	95	96	97	97
16	Height (in)	63.8	64.9	66.8	68.8	70.7	72.4	73.4	63.8	64.9	66.8	68.8	70.7	72.4	73.4
	Height (cm)	162.1	165	169.6	174.6	179.5	183.8	186.4	162.1	165	169.6	174.6	179.5	183.8	186.4
	50th	111	112	114	115	115	116	116	63	64	66	67	68	69	69
	90th	126	127	128	129	131	131	132	77	78	79	80	81	82	82
	95th	130	131	133	134	135	136	137	80	81	83	84	85	86	86
	95th + 12 mmHg	142	143	145	146	147	148	149	92	93	95	96	97	98	98
17	Height (in)	64.5	65.5	67.3	69.2	71.1	72.8	73.8	64.5	65.5	67.3	69.2	71.1	72.8	73.8
	Height (cm)	163.8	166.5	170.9	175.8	180.7	184.9	187.5	163.8	166.5	170.9	175.8	180.7	184.9	187.5
	50th	114	115	116	117	117	118	118	65	66	67	68	69	70	70
	90th	128	129	130	131	132	133	134	78	79	80	81	82	82	83
	95th	132	133	134	135	137	138	138	81	82	84	85	86	86	87
	95th + 12 mmHg	144	145	146	147	149	150	150	93	94	96	97	98	98	99

Adapted from Flynn et al. 2017 [13]

ALN-GO1-001 Protocol Amendment 1**Summary of Changes dated 01 July 2016****Compared to the Original Protocol dated 18 December 2015****A Phase 1/2, Single-Blind, Placebo-Controlled, Single- and Multiple-Ascending Dose Safety, Tolerability, Pharmacokinetic and Pharmacodynamics Study of Subcutaneously Administered ALN-GO1 in Healthy Adult Subjects, and Patients with Primary Hyperoxaluria Type 1****Rationale for Protocol Amendment**

The primary purpose of this amendment is to provide the starting dose of ALN-GO1 for administration to patients with primary hyperoxaluria type 1 in Part B of the study, which is based on preliminary data from Part A of the study in healthy subjects. The Part B starting dose is 1.0 mg/kg, administered every 28 days, the lowest dose determined to have a pharmacological effect in healthy subjects in Part A that was also considered well-tolerated.

Further, in response to feedback from Regulatory Agencies, study cohort progression/escalation and suspension/stopping rules have been included for Part B. These rules apply to adverse events (AEs) considered likely to be related to the underlying disease and for AEs considered possibly or definitely related to study drug. Common Terminology Criteria for Adverse Events criteria will continue to be used to grade AEs. The revised dose escalation rules will be specified to take into consideration the severity of the AEs observed and the frequency of the occurrence of these toxicities within a given cohort in order to authorize dosing in the next cohort (as outlined in Table 1 below). These rules will guide Part B dose escalation and stopping decisions for the cohort by the Safety Review Committee.

The following changes have been made in Part B to streamline and simplify blood sample collections and study evaluations:

- Clarified that the exploratory endpoint [REDACTED]
- Clarified symptom-directed exam specifications and that symptom-directed physical examinations occur during the study, except during Screening and on the last postdose follow-up visit when a full physical examination occurs
- [REDACTED] clarified that eligibility requires a 24-hour urine sample collection [REDACTED]
- Removed requirement for an inpatient stay at the clinical study center for 24-hour urine sample collection, added a 6 hour window for sample collection after study eligibility is confirmed, and clarified the start day for sample collections
- Removed blood and urine sample collection for pharmacokinetic (PK) analyses on Day 141 for patients initially randomized to ALN-GO1 as it is not expected that there will be measureable drug concentrations at this time point postdose

- Removed the Day 2 blood sample collection for pharmacodynamic (PD) analyses as it is not expected that there will be an evident PD effect this soon postdosing
- Added blood and urine sample collections for exploratory ██████████ ██████████ for patients initially randomized to placebo
- Changed the day on which patients will be unblinded to Day 78, rather than Day 85, in order for patients and their families to be better prepared for the transition to receive ALN-GO1 if initially randomized to placebo
- Specified the screening blood pressure criteria for eligibility for patients 6 to 18 years, inclusive, accounting for blood pressure cut-off values for hypertension in children
- Specified that clinical laboratory assessments of liver function tests and serum creatinine will be reviewed locally before study drug administration
- Specified that on days when a blood sample for vitamin B6 should be collected, patients should be instructed to not take vitamin B6 before the blood sample is collected and the study drug is administered
- Removed the 28 day window for the Day 85 study visit indicating that this visit must occur on the scheduled day
- Clarified that additional cohorts may be enrolled at higher, lower, or intermediate dose levels, but will not exceed the maximum administered dose of 6.0 mg/kg
- Updated the procedure for recording serious adverse events (SAEs) in the case report form, with an SAE form as back-up

The following changes have been applied to Part A and Part B to simplify the study:

- Specified that plasma samples, in addition to urine samples, will be collected for assessment of PD parameters
- Increased the overall study duration from 1 year and 8 months to 2 years
- Clarified that the relationship of AEs to study drug will be classified as definitely, possible, unlikely, or not related to study drug; AEs will not be classified as probably related

Additional administrative changes include the following: aligned footnotes in the Schedules of Assessments for Part B (Table 2 and Table 3); moved the blood sample for antidrug antibody analysis from Day -1 to Day 1, and added a blood sample for antidrug antibody analysis at Day 57, for consistency with Part A; added windows for postdose electrocardiograms in Part B; and corrected the time range for pooled urine sample collection for PK analysis on Day 113 and Day 141 from 4-6 hours to 0-4 hours in Part B.

A detailed summary of changes is provided in [Table 1](#). Corrections to typographical errors, punctuation, grammar, abbreviations, and formatting are not detailed. Additionally, updates to the protocol as described in administrative change letters, dated 05 May 2016; 22 February 2016; and 24 February 2016, are not detailed.

Table 1: Protocol Amendment 1 Detailed Summary of Changes

The primary section(s) of the protocol affected by the changes in the amendment are indicated. The corresponding text has been revised throughout the protocol. Deleted text is indicated by ~~strikeout~~; added text is indicated by **bold** font.

Purpose: Provided the starting dose of ALN-GO1 with dose rationale for Part B of the study and that additional cohorts may be enrolled at higher, lower, or intermediate dose levels, but will not exceed the maximum administered dose of 6.0 mg/kg

The primary change occurs in Section 1.4 Dose Rationale

Added: **Preliminary data from Part A suggest that ALN-GO1 is well-tolerated and support selection of the starting dose for the first cohort of Part B of study ALN-GO1-001. The Part B starting dose is 1.0 mg/kg, administered every 28 days, the lowest dose determined to have a pharmacological effect in healthy subjects in Part A that was also considered well-tolerated. The starting dose in Part B is based on data derived from Part A and recommended by the Safety Review Committee (SRC). Additional cohorts may be enrolled at higher, lower, or intermediate dose levels, but will not exceed the maximum administered dose of 6 mg/kg, and will follow the protocol-specified dose escalation criteria.**

Section(s) also containing this change:

- Synopsis
- Section 4.7.2 Study Drug Dosing, Study Progression, and Dose Escalation in Part B

Purpose: Specified that plasma samples, in addition to urine samples, will be collected for assessment of PD parameters

The primary change occurs in Section 3.2, Secondary Endpoints

Now reads: • **Plasma and** urine glycolate concentration

Section(s) also containing this change:

- Synopsis
- Section 1.3, Study Design Rationale
- Section 7.2, Pharmacodynamic Assessments

Purpose: Clarified that the exploratory endpoint [REDACTED]

[REDACTED]

[REDACTED]

[REDACTED] • [REDACTED]

Section(s) also containing this change:

- Synopsis
- Section 7.2, Pharmacodynamic Assessments

Purpose: Increased the overall study duration from 1 year and 8 months to 2 years

The primary change occurs in Section 4.2, Duration of Treatment and Overall Duration of Study

Now reads: The overall duration of the study is estimated to be ~~1 year and 8 months~~ **2 years**, including enrollment.

Section(s) also containing this change:

- Synopsis

Purpose: Changed the day on which patients will be unblinded to Day 78 (from Day 85)

The primary change occurs in Section 4.5 Blinding

Now reads: This is a single-blind, placebo-controlled study; therefore, only the study subjects/patients will be blinded to treatment assignment ~~(up to Day 85 for Part B)~~. **Patients in Part B will be unblinded on or after Day 78 in order for patients and their families to be better prepared for the transition to receive ALN-GO1 if initially randomized to placebo.**

Section(s) also containing this change:

- Synopsis
- Table 2: Schedule of Assessments for Multiple-ascending Dose Cohorts in Patients with Primary Hyperoxaluria Type 1 (Part B)
- Section 4.1.2 Multiple-ascending Dose Part in Patients with Primary Hyperoxaluria Type 1 (Part B)

Purpose: Clarified that the relationship of AEs to study drug will be classified as definitely, possible, unlikely, or not related to study drug

The primary change occurs in Section 4.7.3.1 Cohort Progression/Escalation and Suspension/Stopping Rules in Part A

Now reads: Study cohort progression/escalation and suspension/stopping rules for AEs considered possibly, ~~probably~~, or definitely related to study drug for Part A are described in Table 5. If a subject meets a stopping rule, the subject will be managed as clinically indicated and asked to complete all safety assessments according to the protocol.

Section(s) also containing this change:

- Section 4.7.3.2 Individual Patient Progression/Escalation and Suspension/Stopping Rules in Part B

Purpose: Provided study cohort progression/escalation and suspension/stopping rules for Part B have been included in response to feedback from Regulatory Agencies

The primary change occurs in Section 4.7.3.3 Cohort Progression/Escalation and Suspension/Stopping Rules in Part B

Added: **Study cohort progression/escalation and suspension/stopping rules for AEs considered likely to be related to the underlying disease and for AEs considered possibly or definitely related to study drug for Part B are described in Table 7. If a patient meets a stopping rule, the patient will be managed as clinically indicated and asked to complete all safety assessments according to the protocol. For patients with abnormal renal function consistent with their underlying disease at baseline, evidenced by elevated serum creatinine, the change in this parameter from baseline should be used in grading AEs, rather than laboratory normal values.**

Table 7: Cohort Progression/Escalation and Suspension/Stopping Rules for Part B

Adverse Event(s)	Action
If ≥1 patient in a cohort experiences a severe AE and/or SAE, judged to be possibly or definitely related to study drug	Dosing within that cohort, and in any cohorts receiving a higher dose, will be suspended until SRC review. Following data review, the SRC may permit continuation of any ongoing Part B cohort. Any further dose escalation in a subsequent cohort will be suspended. Resumption of dose escalation will require a substantial amendment, approved by the regulatory authority and relevant ethics committee. However, de-escalation to a lower dose, or intermediate but lower dose, may be allowed by the SRC without a protocol amendment.
If ≥1 patient in Part B experiences a Grade 4 or 5 AE ^a judged to be possibly or definitely related to study drug	Dosing of all patients in Part B will be suspended until SRC review. Resumption of the study will require a substantial amendment, approved by the regulatory authority and relevant ethics committee.

Abbreviations: AE=adverse event; SAE=serious adverse event; SRC=Safety Review Committee.
a Common Terminology Criteria for Adverse Events will be used to grade AEs.

Purpose: Specified the screening blood pressure criteria for eligibility for patients 6 to 17 years, inclusive

The primary change occurs in Section 5.2.2 Additional Exclusion Criteria for Part B

Added: **For patients aged 6 to 11 years, inclusive, males with systolic blood pressure >115 mmHg and/or a diastolic blood pressure >75 mmHg and females with systolic blood pressure >110 mmHg and/or a diastolic blood pressure >75 mmHg after 10 minutes of rest at screening. For male and female patients aged 12 to 17 years, inclusive, systolic blood pressure >120 mmHg and/or a diastolic blood pressure >80 mmHg after 10 minutes of rest at screening.**

plasma glycolate concentration.

Options for the providing 24-hour urine collections, patients will have the option to bring the urine collection to the clinical study center at specified PD follow-up visits, courier samples to the clinical study center or vendor performing analyses, or have the 24-hour urine collected during an inpatient stay at the clinical study center for other assessments. are in Section 7.1.1.1.

Section(s) also containing this change:

- Table 2: Schedule of Assessments for Multiple-ascending Dose Cohorts in Patients with Primary Hyperoxaluria Type 1 (Part B)
